9.4 Safety and Tolerability Assessments

9.4.1 Adverse events

Where changes in severity are recorded in the Case Report Form (CRF), each separate severity of the adverse event (AE) will be reported in the listings, only the most severe will be used in the summary tables. A pre-existing condition is defined as an AE that starts before the subject has provided written informed consent and is ongoing at consent. A non-treatment emergent AE is defined as an AE which starts after informed consent but prior to dosing. A treatment-emergent AE is defined as an AE which occurs postdose or which is present prior to dosing and becomes more severe postdose.

All AEs will be listed. Treatment-emergent AEs will be summarized by treatment, severity and relationship to the study drug. The frequency (the number of AEs, the number of subjects

experiencing an AE and the percentage of subjects experiencing an AE) of treatment-emergent AEs will be summarized by treatment, Medical Dictionary for Regulatory Activities (MedDRA) version 19.1 system organ class and preferred term. The summary and frequency AE tables will be presented for all causalities and those considered related to the study drug. Any serious AEs will be tabulated.

9.4.2 Concomitant medication

Concomitant medication will be coded using the WHO drug dictionary (Version September 2016). Concomitant medication will be listed.

9.4.3 Clinical laboratory parameters

All clinical chemistry and hematology data will be summarized by parameter and treatment, and listed. Urinalysis data will be listed. Additionally clinical chemistry, hematology and urinalysis data outside the reference ranges will be listed.

Values for any clinical chemistry, hematology and urinalysis values outside the reference ranges will be flagged on the individual subject data listings.

9.4.4 Vital signs

Vital signs data will be summarized by treatment together with changes from baseline, where baseline is defined as Day 1 predose. Figures of mean vital signs and mean changes from baseline profiles by treatment will be presented by treatment. Furthermore, values for individual subjects will be listed.

9.4.5 Electrocardiogram (ECG)

The ECG data will be obtained directly from the 12-lead ECG traces. These data include the PR, QT, QTcB intervals, QRS duration and heart rate, where QTcB is the QT interval corrected using Bazett's formula. In addition, QTcF (the QT interval corrected using Fridericia's formula) will be calculated as follows:

$$QTcF = \frac{QT}{\sqrt[3]{(60/HR)}}$$

The ECG data will be summarized by treatment together with changes from baseline, where baseline is defined as Day 1 predose. Figures of mean ECG data and mean changes from baseline will be presented by treatment.

9.4.6 Injection/Infusion Site Assessment

Injection/infusion site assessment data (erythema, induration, categorical pain, pruritus and edema) will be listed and summarized in frequency tables.

9.4.7 Injection Site Pain Assessment

Injection site pain will be assessed using the Visual Analog Scale (VAS) and listed and summarized by treatment (performed only on subjects randomized to Test SC 2 × 1 mL and Test SC 1 × 2 mL).

9.4.8 Injection Site Leakage

Injection site leakage data will be listed. Any bleeding from injection site will also be documented (performed only on subjects randomized to Test SC 2 × 1 mL and Test SC 1 × 2 mL).

9.4.9 Immunogenicity

Immunogenicity data will be listed and frequency tables will be presented. The frequency of treatment-emergent anti-drug antibodies (ADAs) will also be calculated. Treatment-emergent ADAs are those that are induced or boosted by exposure to study drug, with a 4-fold increase in titer compared to baseline if ADAs were detected at baseline or a titer 2-fold greater than the minimum required dilution (1:10) if no ADAs were detected at baseline.

To show the association of treatment -emergent ADAs with adverse events, the frequency of treatment-emergent ADAs will be presented by MedDRA preferred term. Relationship between the presence of antibodies and the PK parameters of LY3074828 may be assessed graphically.

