| Vital signs: blood pressure, pulse rate, temperature (hour) | X | | Predose, end of infusion ^b , 2, 6 | 24 | 72 | 168 | 240 | 336 | 504 | 672 | 1008 | | | 2016 | X | Times are referenced to start of dosing. Single ECGs will be collected. Time allowance for 2, 6, and 24 hour time points will be ±15 minutes, ±30 minutes and ±90 minutes respectively. End of infusion vital signs and ECG should be taken 5 to 15 minutes after the end of infusion. |
| 12-lead ECG (hour) | X | | Predose, end of infusion ^b , 2, 6 | 24 | 72 | 168 | | 336 | | 672 | | | | 2016 | X | |
| Physical examination / Medical assessment | X | X | | X | | | | | | | | | | X | X | Full physical examination/ medical assessment at screening, Day -1, ED. Symptom directed physical examination/ medical assessment at all other time points, and as deemed necessary by the investigator. |
| AE review | X | X | X | X | X | X | X | X | X | X | X | X | X | X | X | AE only after signing ICF |
| QuantiFERON®-TB Gold test | X | | | | | | | | | | | | | | | |
| Pregnancy test ^c | X | X | | | | | | | | X | | X | | X | X | Women of childbearing potential only. Serum pregnancy test at screening, urine at other times. A positive urine pregnancy test will be confirmed with a serum pregnancy test. |
| Clinical laboratory tests | X | X | | | X | | | | X | | X | | X | X | X | Urine ethanol and drug screen performed at screening and Day -1 during CRU |

| Study Day | Screening ≤ 28 days | -1 | 1 | 2 | 4 ± 1 d | 8 ± 1 d | 11 ^a ± 2 d | 15 ± 2 d | 22 ± 2 d | 29 ± 2 d | 43 ± 2 d | 57 ± 3 d | 71 ± 3 d | 85 ± 3 d | FU/ED ^d | Comment |
|---|--------------------------|----|---|----|-------------|-------------|---------------------------|--------------|--------------|--------------|--------------|--------------|--------------|--------------|--------------------|--|
| | | | | | | | | | | | | | | | | admission, and may be repeated at the discretion of the investigator. |
| LY3074828 dose | | | X | | | | | | | | | | | | | |
| Injection / infusion-site assessment for erythema, induration, categorical pain, pruritus, and edema (hour) | | | 0, 0.25 ^e , end of infusion ^b | 24 | | 168 | | 336 | | | | | | | | Times are referenced to start of dosing. 0 hour assessments should be performed within 5 minutes after giving all SC injections or start of IV infusion. End of infusion assessments should be completed within 5 minutes after infusion. Additional assessments may be performed if deemed necessary by the investigator. |

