LY3074828 is a humanized immunoglobulin G4-variant monoclonal antibody that is directed against the p19 subunit of IL-23 and does not bind IL-12. LY3074828 is being developed for the treatment of autoimmune diseases in which the IL-23 pathway is thought to have a significant pathogenic role. LY3074828 does not bind rodent IL-23, so a surrogate molecule was developed to neutralize mouse IL-23 for use in preclinical studies. Neutralization of IL-23 with this surrogate antibody significantly reduced the development of arthritis and inhibited ileal inflammation in a mouse model of spondyloarthropathy with bowel inflammation (Ruutu et al. 2012). In addition, neutralization of IL-23 significantly reduced the disease score in the relapsing-remitting experimental autoimmune encephalomyelitis (multiple sclerosis-like) model in mice. Anti-IL-23 antibody also demonstrated some efficacy in preclinical arthritis models, depending on the timing of intervention (Cornelissen et al. 2013).

Study I6T-MC-AMAA (AMAA), has been completed to date evaluating LY3074828 in healthy volunteers and in subjects with plaque psoriasis. Seven cohorts of subjects with active psoriasis received single doses of IV LY3074828 (up to 600 mg) or placebo. A single cohort of 5 healthy subjects received single SC doses of LY3074828 (120 mg). A total of 33 subjects with psoriasis and 5 healthy subjects were administered LY3074828. Seven subjects with psoriasis received placebo.

- No serious adverse events (SAEs) were reported. Treatment-emergent adverse events (TEAEs) reported as related to investigational product included one Grade 1 event of diarrhea experienced by a single subject in the 5-mg IV cohort, 2 Grade 1 events of nausea experienced by 2 subjects in the 20-mg IV cohort, one Grade 1 event of headache experienced by a single subject in the 200-mg IV cohort, and five Grade 1 events of injection site pain experienced by 3 subjects in the 120-mg SC cohort. No LY3074828 TEAEs of Grade 2 or higher were reported. No dose-dependent trends in adverse events (AEs) were seen. No clinically important changes in vital signs, electrocardiograms (ECGs), or clinical laboratory results were observed.

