9.4.7. Immunogenicity Assessments

Blood samples for immunogenicity testing will be collected to determine antibody production against the investigational product as specified in the Schedule of Activities (Section 2).

A risk-based approach will be used to monitor subjects who develop TE-ADAs during and following treatment with LY3074828. TE-ADAs are defined as either 2-fold increase in titer (i.e. 1:20) above the minimum required dilution (1:10) if no ADAs were detected at baseline or a 4-fold or greater increase in titer over baseline for subjects that are ADA positive at baseline. LY3074828 is a monoclonal antibody that binds to p19 of IL-23, and there is no unique/non-redundant endogenous protein counterpart, greatly minimizing the risk of cross-reactive ADA. Any potential risks of ADA development following this single dose trial would be dependent on LY3074828 exposure outside of this clinical trial. The largest potential risk would be reaction upon subsequent drug exposure that could range in severity from mild local injection site reactions to systemic anaphylaxis and/or systemic immune complex disease (Arthus-reaction). These potential risks would likely be associated with higher serum concentrations of ADA.

Given that the subjects have only a single exposure to LY3074828, any ADA response is anticipated to peak and then diminish due to lack of additional exposures. Subjects will have ADA sampling at baseline, Day 15, Day 29, Day 85, and at follow-up. Subjects that are observed to have significant (i.e. greater than 1:1000 titer) and non-decreasing titers that meet the definition of TE-ADA, will be requested to return every 3 months after the last sample to have follow-up ADA samples tested until the titer has returned to within 1 titer of their baseline or is clearly trending back to the baseline titer. The rationale for the definitions of both TE-ADA and return to baseline is based on the premise that a 1-titer change may result from expected assay variability.

Subjects followed for at least 1 year since last dose who have not returned to baseline, as defined above, will be assessed for safety concerns and, if no clinical sequelae are recognized by the clinical team, no further follow-up will be required. Subjects who have clinical sequelae that are considered potentially related to the presence of TE-ADA may also be asked to return for additional follow-up testing.

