10.3.5. Evaluation of Immunogenicity

The frequency of antibody formation to LY3074828 will be determined. Treatment-emergent ADAs are those that are induced or boosted by exposure to study drug, with a 4-fold increase in titer compared to baseline if ADAs were detected at baseline or a titer 2-fold greater than the minimum required dilution (1:10) if no ADAs were detected at baseline.

If a neutralization assay is performed, the frequency of neutralizing antibodies will be determined. The relationship between the presence (or absence) of antibodies and clinical parameters (AEs) will be assessed. Likewise, the relationship between the presence of antibodies and the PK parameters to LY3074828 will be assessed.

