11. CHANGES FROM THE PROTOCOL SPECIFIED STATISTICAL ANALYSES

There were no changes from the protocol specified statistical analyses.

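### SAP 9.4.9's one antibody-by-adverse-event output has no antibody-negative group, treatment split or AE onset, so on its own it does not deliver the relationship Protocol 10.3.5 commits to (low severity)

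*SAP*

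**What the plan says.** Protocol 10.3.5 states: "The relationship between the presence (or absence) of antibodies and clinical parameters (AEs) will be assessed". SAP 9.4.9 gives the purpose of its output as "To show the association of treatment -emergent ADAs with adverse events", and the output itself is that "the frequency of treatment-emergent ADAs will be presented by MedDRA preferred term". The other antibody outputs in 9.4.9 are listings, frequency tables with an overall TE-ADA frequency, and an optional graph against PK. SAP 11 says: "There were no changes from the protocol specified statistical analyses". SAP 3 says that the SAP supersedes the protocol's statistical considerations and that substantial differences will be identified. It also says that table layouts are held in a separate shell document.

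On timing, Protocol 9.4.7 states: "Subjects will have ADA sampling at baseline, Day 15, Day 29, Day 85, and at follow-up". SAP 9.4.1 states: "A treatment-emergent AE is defined as an AE which occurs postdose". The Schedule of Activities (Protocol Section 2) solicits site symptoms from dosing: "0 hour assessments should be performed within 5 minutes after giving all SC injections or start of IV infusion". Under Protocol 9.4.6, any such symptom leads to one AE record for a site reaction.

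**The concern.** Presence or absence of antibodies is a two-group question: how often an AE occurs in TE-ADA-positive subjects, and how often in TE-ADA-negative subjects. A table of TE-ADA frequency under each preferred term describes only the antibody status of subjects who had the term. A term may collect TE-ADA-positive subjects because it is common, with no link to antibodies.

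Two further features are missing from the text. There is no split by treatment, yet site reactions depend on route. In Study AMAA (Protocol 3.2) the three TE-ADA cases all followed IV dosing, while the injection-site pain was in the SC cohort, so pooling over routes could hide or create a pattern. There is also no reference to onset. A reaction minutes after injection and a hypersensitivity event after seroconversion would count alike.

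TE-ADA incidence is a secondary tolerability endpoint. Its incidence is unaffected. What is at stake is how its clinical relevance is described in the study report.

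**Working it through.** **1. When a treatment-emergent antibody can first be seen.** Protocol 9.4.7 lists baseline, Day 15, Day 29, Day 85 and follow-up, which is 5 samples. Protocol Appendix 4 allows 5 immunogenicity samples of 10 mL, and 5 × 10 = 50 mL, its stated total. The figures agree, so no scheduled sample lies between predose and Day 15. The plan gives no figure for the antibody-by-AE output itself.

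**2. What a count under a term can and cannot tell.** Assume 6 TE-ADA-positive and 66 TE-ADA-negative subjects (6 is 72 × 3/38 = 5.7, rounded; see step 4), and 3 positive subjects with a given term.

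| Positive with term | Negative with term | Difference in AE incidence | TE-ADA % among subjects with term |
|---|---|---|---|
| 3/6 (50%) | 33/66 (50%) | 0 points | 3/36 = 8.3% |
| 3/6 (50%) | 3/66 (4.5%) | +45 points | 3/6 = 50% |
| 3/6 (50%) | 60/66 (90.9%) | −41 points | 3/63 = 4.8% |

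The count of 3 fits no association, a positive one or an inverse one. If a percentage of subjects with the term is shown (last column), setting it beside the overall TE-ADA frequency of 6/72 = 8.3% gives the direction.

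**3. Chance co-occurrence.** With no association, the expected number of subjects with both the term and TE-ADA is N × r × p, where r is the TE-ADA rate and p the term incidence. The three SC arms give N = 3 × 18 = 54. Both rates are assumptions.

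- Low end: 54 × 0.03 × 0.10 = 0.16.
- High end: 54 × 0.20 × 0.60 = 6.5.
- Illustration: r = 3/38 = 7.9% (3 TE-ADA cases among 33 + 5 dosed in AMAA) and p = 3/5 = 60%, from "five Grade 1 events of injection site pain experienced by 3 subjects in the 120-mg SC cohort". Then 54 × 0.079 × 0.60 = 2.6. About 54 × 0.60 × 0.921 = 29.8 TE-ADA-negative subjects would have the same event and not be shown.
- Near 0: Protocol 3.2 reports no TE-ADA after SC dosing in AMAA (0 of 5), and no infusion or injection-site reactions in Study AMAD, which included a 200 mg SC dose. Setting r = 0 for SC subjects, or p = 0 for site reactions, makes the product 0.

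**4. What the corrected table would contain.** At 3/38, 72 × 0.079 = 5.7 TE-ADA-positive subjects. The exact 95% CI for 3/38 is 1.7% to 21.4%, or about 1 to 15 of 72. With 6 against 66, a two-sided 5% Fisher test has about 60% power for 50% v 10% and about 23% for 30% v 10%. That is too little for a useful test.

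**The case against.** The strongest reply is that the pieces are already planned. SAP 9.1 calls for counts and percentages of categorical data. If the percentage is TE-ADA-positive among subjects with the term, a common unrelated AE shows roughly the overall TE-ADA rate, not an inflated one. The negative counts also follow by subtraction: in the first row of the table above, 36 subjects with the term minus 3 positive gives 33, and 72 minus 6 gives 66. SAP 9.4.1 supplies subjects per term, and 9.4.9 the overall TE-ADA frequency. All AEs and immunogenicity data are listed, and with so few positive subjects a case-by-case review is feasible. The shells may already have columns by antibody status.

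Most of this stands, and it limits the point. A reader might infer that the SAP cannot show an association at all, or that the commonest AE must look most associated. The documents do not support either, because 9.4.9 leaves the denominator open and direction can be partly rebuilt. A reader might also infer that Day 1 events precede any detectable antibody. That is not so: TE-ADA includes boosted responses, and those subjects are already ADA-positive predose. What can be said is that Day 1 events precede the first sample that could show a treatment-emergent response.

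The reply does not remove the gap. Subtraction gives no timing, and the listings give it only if they carry onset and sample dates. It gives no split by treatment unless the antibody table is split too. The reader should not have to rebuild the analysis that the protocol promised.

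**Conclusion.** The point holds for the SAP text, at low severity. Its only antibody-by-AE output does not by itself show the relationship that Protocol 10.3.5 commits to, yet no change is declared. Whether the shells fill the gap is unknown.

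The size is uncertain. About 0.2 to 6.5 chance co-occurrences in 54 SC subjects follows from assumed rates. The 2.6 illustration combines an antibody rate seen only after IV dosing with a pain rate from 5 subjects, so it is not a forecast. The figure is near 0 if the SC antibody result in AMAA or the injection-site result in AMAD carries over. The primary PK analysis and the TE-ADA incidence endpoint are not affected.

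**What to change.** Replace the association sentence in SAP 9.4.9 with:

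> The number and percentage (n/N) of subjects with each treatment-emergent AE preferred term will be presented for TE-ADA-positive and TE-ADA-negative subjects, by treatment and overall. For TE-ADA-positive subjects, AE onset day will be listed alongside the date of the first TE-ADA-positive sample and of the preceding ADA sample, and AEs with onset before the first TE-ADA-positive sample will be flagged.

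Flagging is preferable to excluding, because seroconversion may fall anywhere between the two samples. Cutting at the last negative sample would not work. For a baseline-negative subject first positive on Day 15, that sample is the predose one, so Day 1 events would stay in. A boosted subject may have no negative sample at all.

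Keep the output descriptive, with no test, in line with SAP 9.4.11. The cost is one sentence, one revised table and one listing, with no new data. The downside is very small cells, more so by treatment.

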9.4.10 Other assessments

All other safety assessments not detailed in this section will be listed but not summarized or statistically analyzed.

9.4.11 Safety and Tolerability Statistical Methodology

No inferential statistical analyses are planned.

10. INTERIM ANALYSES

The Lilly study team and investigator will be unblinded. Data may be accessed and analyzed while the trial is ongoing, but no changes to the study design are planned. An assessment committee will not be formed.

Interim analysis is scheduled to occur when safety and PK data through approximately Day 57 (8 weeks postdose) become available from enrolled subjects from each treatment. The purpose of the interim analysis is to: trigger Chemistry, Manufacturing, and Control processes with respect to LY3074828 formulation; trigger the formal bridging study; and to inform dose selection for Phase 3 first registration.

11. CHANGES FROM THE PROTOCOL SPECIFIED STATISTICAL ANALYSES

There were no changes from the protocol specified statistical analyses.

13. DATA PRESENTATION

13.1 Derived Parameters

Individual derived parameters (e.g. PK parameters) and appropriate summary statistics will be reported to three significant figures. Observed concentration data, e.g. C_{max} , should be reported as received. Observed time data, e.g. t_{max} , should be reported as received. N and percentage values should be reported as whole numbers. Median values should be treated as an observed parameter and reported to the same number of decimal places as minimum and maximum values.

13.2 Missing Data

Missing data will not be displayed in listings.

